3.1 Inclusion Criteria

Informed Consent and Willingness to Participate

___1. Documented informed consent of the participant and/or legally authorized representative.

- Assent, when appropriate, will be obtained per institutional guidelines

Nature of Illness and Illness Related Criteria

___2. Histologically confirmed mantle cell lymphoma with documentation of monoclonal CD20+ B cells that have a chromosome translocation t(11;14)(q13;q32) and/or overexpress cyclin D1.

___3. Age \geq 65 years; or \geq 50 years and deemed ineligible for aggressive induction therapy or autologous stem cell transplant by the investigator, or unwilling to undergo aggressive induction; or \geq 18 years with documented del(17p), or TP53 mutation, or complex karyotype (CK) by cytogenetics and/or FISH studies.

___4. Requiring treatment for MCL, and for which no prior systemic anticancer therapies have been received (local radiotherapy not exceeding a total dose of 20 Gy at least 2 weeks prior the first dose of study therapy is allowed).

___5. Measurable disease by CT or PET/CT scan with one or more sites of disease \geq 1.5 cm in longest dimension (including splenomegaly), or bone marrow involvement with or without malignant lymphocytosis.

___6. ECOG \leq 2 ([Appendix A](#)).

Clinical Laboratory and Organ Function Criteria

___7. Without bone marrow involvement: ANC \geq 1000/mm ³ With bone marrow involvement: ANC \geq 500/mm ³ NOTE: Growth factor is not permitted within 7 days of ANC assessment unless cytopenia is secondary to disease involvement.	ANC:	Date:
___8. Without bone marrow involvement: Platelets \geq 75,000/mm ³ With bone marrow involvement: Platelets \geq 30,000/mm ³ NOTE: Platelet transfusions are not permitted within 7 days of platelet assessment unless cytopenia is secondary to disease involvement.	Plts:	Date:
___9. Total bilirubin \leq 1.5 X ULN or \leq 3X ULN for Gilbert's disease.	ULN: Bil:	Date:
___10. AST \leq 2.5 x ULN	ULN: AST:	Date:
___11. ALT \leq 2.5 x ULN	ULN: ALT:	Date:

Patient MRN (COH Only)	Patient Initials (F, M, L):
Institution:	

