- p. Bone marrow biopsies will be performed at the following time points if feasible (please contact Study PI if bone marrow collection is not feasible at either time point to receive a waiver):
 - 1- At baseline** (during screening). If a patient had a recent bone marrow biopsy (within 90 days), this time point may be omitted after a discussion with the Study PI. In this case, a correlative sample will not be submitted.
 - 2- At the time a CR is suspected** based on imaging results (within 8 weeks after such result).
 - 3- At the time of disease relapse.**
- At each time point, bone marrow samples will be collected for correlative studies ([Section 9.1.2](#)).
- q. Every other cycle starting on C8D1 (i.e. on days of ublituximab infusion).
- r. Ublituximab infusions are on Day 1 of C8, C10, C12, C14, C16, C18, C20, C22, C24, C26, C28, and C30.
- s. Disease assessments (imaging) to occur on Days 1 (\pm 7 days).
- t. PET-CT is strongly preferred. CT in lieu of PET-CT is allowed if patient is in CR and CR was already confirmed by PET-CT, and for patients for whom PET-CT is not feasible (with Study PI's approval).
- u. Every 6 months (+/- 2 weeks) from last on treatment scan until end of protocol therapy.
- v. NGS panel (HopeSeq at City of Hope), FISH analysis, conventional cytogenetics and IHC should be performed on tumor diagnostic material (lymph node, bone marrow, peripheral blood) based on disease characteristics, per institutional practice standards at screening. Every effort should be made to collect such data ([Section 9.3](#)).
- w. Serum virology to include HBsAg, HBc antibody, HCV antibody and CMV IgG and IgM (or may do CMV by PCR at investigator discretion). If HBc antibody, HCV antibody or CMV IgG or IgM is positive, subject must be evaluated for the presence of active HBV, HCV or CMV by PCR.
- x. CMV screening by PCR for all subjects receiving study treatment beginning in Cycle 4 and approximately every 3 to 4 cycles thereafter aligned with study visits.
- y. This time point serves as TLS assessment. TLS assessment will be performed on Day 2 (+ 1 day).
- z. Activities to be performed on D15 +/- 3 days.

* EOM = End of maintenance. Visit to occur at the end of Cycle 25 (with a +7 days window) and to include disease assessment (imaging).

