11.0 ENDPOINT DEFINITIONS/MEASUREMENT OF EFFECT

11.1 Assessment of Response

Lymphoma response/progression will be evaluated using 2014 Lugano Classification (see [Appendix C](#)). [51]

Disease assessment will be performed by PET-CT. In patients in whom PET-CT is not feasible, CTs may be used in place of a PET-CT after discussion with the Study PI ([name]). Patients must have a bone marrow biopsy performed at baseline and to confirm CR (if suspected based on imaging). After CR, additional bone marrow biopsy is only required if clinically indicated and at relapse. Additional necessary restaging studies including dedicated CT scans or MRI, are permitted at the investigator's discretion. PET-CT and CT results will be read by a radiologist at each study site and investigator response assessment will be performed.

For patients with progression of disease on imaging, it is strongly recommended that a confirmatory biopsy be obtained whenever possible.

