11.2 Primary Endpoint(s)

Complete response (CR) rate: defined as the proportion of response-evaluable participants (see [Section 12.2](#)) that achieve a CR at the end of induction therapy. If a patient achieves CR earlier during induction therapy but is PD at the end of induction, the patient will be considered end of induction non-CR. If a patient achieves a CR earlier during induction but does not have a response evaluation at the end of induction for some reason (for example early termination of induction due to patient refusal), the prior CR will be carried over as the end of induction CR.

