12.0 STATISTICAL CONSIDERATIONS

12.1 Study Design

This is a multicenter, single-arm Phase 2 study evaluating AU2 therapy for patients with previously untreated MCL. Patients will first receive 6 cycles of AU2 (acalabrutinib + umbralisib + ublituximab) induction; those who achieve SD or better response after induction will then receive 19 cycles of maintenance with the 3 agents, during which ublituximab will only be given every 2 cycles. Each cycle will be 28 days. Participants may continue therapy with acalabrutinib beyond 25 cycles of Induction + Maintenance therapy at the treating physician's discretion. Response will be evaluated just prior to C4, C7 (End of Induction), C14, C20 , EOM (end of maintenance), every 6 months thereafter until end of protocol therapy (if patient continues with oral agents only beyond 25 cycles), and at Safety visit.

The primary endpoint is complete response (CR) rate after AU2 induction therapy. Secondary endpoints include toxicities of AU2 induction and maintenance therapy, overall response rate to protocol therapy, duration of response, progression free survival, and overall survival.

The study sample size is based on the desire to discriminate a promising CR rate of 50% (alternative hypothesis) from a disappointing CR rate of 25% (null hypothesis) after AU2 induction. These response rates were chosen because 1) BR, a current standard, has been associated with an ORR of 80-90% and a CR rate of 40% [5, 7]; 2) In the phase 2 ACE-LY-004 trial in R/R MCL, treatment with acalabrutinib was associated with an ORR of 81% and a CR rate of 40% [39]. However, it is anticipated that this study will enroll a higher proportion of patients with high-risk MCL (*TP53* aberrations, CK) where BR is ineffective.

Simon's optimal two-stage design will be used. In the first stage, 9 evaluable patients will be accrued. If there are 2 or fewer CRs in these 9 patients, the study will be stopped. Otherwise, 15 additional evaluable patients will be accrued for a total of 24. The null hypothesis will be rejected and AU2 induction therapy will be considered promising if 10 or more CRs are observed in 24 evaluable patients. This design yields a 1-sided type I error rate of 0.05 and power of 0.8. When the CR rate is disappointing (25%), there is an 60% chance that the study will be terminated after the first stage.

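### Does the waivable marrow biopsy leave the primary CR endpoint without a scoring rule?

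*Combined protocol and SAP*

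**What the plan says.** Section 11.1 first sets the rule for response: the 2014 Lugano Classification as laid out in Appendix C. It then adds "Patients must have a bone marrow biopsy performed at baseline and to confirm CR (if suspected based on imaging"). After CR, it asks for further marrow sampling only when clinically indicated and at relapse.

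Footnote p of the Study Calendar (section 10.0) is softer: "Bone marrow biopsies will be performed at the following time points if feasible". It lists baseline, suspected CR (within 8 weeks of the imaging result) and relapse, and provides for a Study PI waiver: "please contact Study PI if bone marrow collection is not feasible at either time point to receive a waiver". Its reference to either time point sits above a list of three, which is a clerical slip.

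Footnote t strongly prefers PET-CT but permits CT in two situations. One is when PET-CT is not feasible. The other reads "CT in lieu of PET-CT is allowed if patient is in CR and CR was already confirmed by PET-CT".

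Section 11.2 defines the primary endpoint as the proportion of response-evaluable participants "that achieve a CR at the end of induction therapy". It settles two special cases. An earlier CR followed by progression at the end of induction is non-CR. An earlier CR is carried forward if the patient "does not have a response evaluation at the end of induction for some reason". Section 12.1 fixes the timing: "Response will be evaluated just prior to C4, C7 (End of Induction").

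In Appendix C the marrow line for CR depends on the scan. The PET-CT column asks for no FDG-avid marrow disease. The CT column asks for normal morphology, with immunohistochemistry if indeterminate. Inclusion criterion 5 admits measurable disease on imaging "or bone marrow involvement with or without malignant lymphocytosis".

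**The concern.** Read side by side, section 11.1 makes the biopsy a condition of CR, footnote p lets it be waived, and footnote t speaks as if PET-CT alone confirms CR. Section 12.2 keeps an unbiopsied patient in the denominator, since one cycle and one post-baseline disease evaluation are enough. Nothing states whether that patient enters the numerator.

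Two routes look especially awkward.

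1. **Scan type.** A patient in PET-CT CR at C4D1 may be restaged by CT at C7D1, the primary time point. Without a biopsy, the PET-CT marrow line can be met and the CT line cannot. The carry-forward rule does not apply, because an evaluation exists, and the downgrade rule does not apply, because there is no progression.
2. **Marrow-only disease.** If a patient enters on marrow involvement that is not FDG-avid, the PET-CT lines for CR are met before treatment. Only the waivable biopsy can then show a response.

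The cut-offs are small counts: 3 of 9 to continue and 10 of 24 to call the regimen promising. One patient can reverse either decision. Response is investigator-assessed, the trial is open-label, and the Study PI grants the waivers.

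**Working it through.** **Reproducing the design.** Inputs from section 12.1: null rate 0.25, alternative 0.50, continue with 3 or more CRs in 9, reject the null with 10 or more in 24. The probability of rejection at CR rate p is the sum over x = 3 to 9 of P(X₁ = x) × P(X₂ ≥ 10 − x), with X₁ ~ Bin(9, p) and X₂ ~ Bin(15, p).

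- p = 0.25: 0.0485 (stated 0.05)
- p = 0.50: 0.8055 (stated 0.8)
- P(X₁ ≤ 2) at p = 0.25: 0.6007 (stated 60%)

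The concern disputes none of these figures.

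**Assumptions.** The documents give no frequency for waived or missed biopsies. Let u be the share of imaging CRs without a biopsy, taken as 5% or 10%. Let m be the share of imaging CRs that are marrow-positive, taken as 10% or 20%. At u = 0 every effect below is zero.

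**(a) Unbiopsied CRs scored by Appendix C, true rate 0.25.** Counted rate = 0.25 × [1 + u·m/(1 − m)].

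| u | m | counted rate | type I error |
|---|---|---|---|
| 5% | 10% | 0.2514 | 0.0501 |
| 5% | 20% | 0.2531 | 0.0523 |
| 10% | 10% | 0.2528 | 0.0519 |
| 10% | 20% | 0.2563 | 0.0563 |

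**(b) Unbiopsied CRs all scored as non-CR.** Counted rate = q(1 − u), where q is the imaging CR rate and biopsied CRs are taken as confirmed. The strict count never exceeds the imaging count, so the difference in rejection probability is the chance that the two readings reach opposite conclusions.

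| q | all counted | strict, u = 5% | strict, u = 10% | chance of opposite conclusions |
|---|---|---|---|---|
| 0.50 | 0.8055 | 0.7366 | 0.6559 | 0.069 to 0.150 |
| 0.40 | 0.4705 | 0.3937 | 0.3196 | 0.077 to 0.151 |
| 0.25 | 0.0485 | 0.0352 | 0.0248 | 0.013 to 0.024 |

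**(c) Scan-type route, q = 0.50.** If a share c of unbiopsied CRs have CT at C7D1 and are scored afresh by the CT column, the rate is 0.50 × (1 − c·u).

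- c = 50%: 0.4875 (u = 5%) and 0.475 (u = 10%), so power is 0.7727 and 0.7366.
- c = 10%, u = 5%: 0.4975, power 0.7992.
- c = 20%, u = 10%: 0.49, power 0.7795.

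C4D1 to C7D1 is nominally 3 × 28 = 84 days. The biopsy prompted by a C4D1 CR is due within 56 days of the result, so it is normally in hand about 28 days before the primary assessment.

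**(d) Marrow-only route.** If a share f of patients enter on non-avid marrow disease alone and 10% of them are unbiopsied and counted as CR, the rate is 0.25 + f × 0.10 × 0.75.

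- f = 1%: 0.25075, type I error 0.0494
- f = 2%: 0.2515, type I error 0.0503
- f = 5%: 0.25375, type I error 0.0531
- f = 10%: 0.2575, type I error 0.0580

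**The case for a change.** The strongest argument for a change is that two competent statisticians could score the same data differently. A requirement in section 11.1 that a biopsy confirm CR has little force for PET-CT patients if the Appendix C marrow line is enough without it. At 5-10% unbiopsied, the two readings disagree in 0.069-0.150 of trials when the imaging CR rate is 50%. The remedy would cost a few sentences, and a rule chosen after results are known invites criticism.

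Part of this stands. The wording in section 11.1 and in footnotes p and t is not aligned, no sentence names the unbiopsied imaging CR, and with cut-offs this small one patient can matter.

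The rest is weaker.

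- A general requirement with a controlled exception is ordinary protocol structure. Once the biopsy is waived, the named criteria still apply. The large disagreement in (b) arises only against a reading in which a granted waiver automatically makes the patient a failure. It measures the distance between two readings and is not an error rate of the plan.
- Footnote t reads most naturally as follow-up of a CR already established by PET-CT. Fresh scoring by the CT column would also fail a patient with a residual node above 1.5 cm, which the PET-CT column accepts, even with a negative biopsy. That is unlikely to be what was meant. It also shows that the difference between scan types is not specific to marrow, so a rule on the marrow line alone would not remove it.
- The marrow-only route needs disease confined to marrow, not avid at baseline, not biopsied, and then scored by a column that had nothing to measure. Section 2.1.1 describes most patients as presenting with stage IV disease that often includes enlarged nodes and spleen.

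**Conclusion.** No change to the plan follows. The mismatch between section 11.1 and footnote p is real, but it leaves a missing detail and does not make a stated rule or figure wrong. Appendix C, which section 11.1 makes the basis of scoring, settles most unbiopsied patients. A sensible analyst would keep the PET-CT-based status of a patient followed by CT without progression, and would not call a marrow-only patient CR without marrow evidence.

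Under that reading the type I error is 0.050-0.056 for 5-10% unbiopsied and 10-20% marrow-positive, against 0.0485 as designed, and power stays near 0.806. The opposite direction, counting every unbiopsied CR as a failure, protects against marrow-positive false CRs at the price of power of 0.737-0.656. The documents do not give the marrow rules behind the 40% benchmark CR rates, so neither direction can be shown to be the like-for-like comparison. The choice is a fair trade-off.

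All these sizes rest on assumed frequencies. If biopsies are rarely waived or missed, the issue all but disappears. The sample size of 24 and both decision rules stand as written.

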- Malabsorption syndrome, disease significantly affecting gastrointestinal function, or resection of the stomach or small bowel that is likely to affect absorption, symptomatic inflammatory bowel disease, partial or complete bowel obstruction, or gastric restrictions and bariatric surgery, such as gastric bypass.
- Presence of a gastrointestinal ulcer diagnosed by endoscopy within 3 months before screening.
- Known bleeding disorders (e.g., von Willebrand's disease or hemophilia).
- History of significant cerebrovascular disease/event, including stroke, myocardial infarction, or intracranial hemorrhage, within 6 months prior to start of protocol therapy.
- Known active central nervous system (CNS) involvement by lymphoma, including leptomeningeal involvement.
- Clinically significant cardiovascular disease such as symptomatic arrhythmias, congestive heart failure, or myocardial infarction within 6 months of screening, or any Class III or IV cardiac disease as defined by the New York Heart Association Functional Classification. Note: Subjects with controlled, asymptomatic atrial fibrillation can enroll on study.
- Unstable angina (angina symptoms at rest), new-onset angina (begun within the last 6 months).
- History of or current progressive multifocal leukoencephalopathy (PML).
- Inability to swallow and retain an oral medication.
- Clinically significant uncontrolled illness, including active infection requiring antibiotics or antiviral agents.
- Live virus vaccines within 4 weeks of start of protocol therapy or planned administration of live virus vaccines during ublituximab therapy.
- Evidence of chronic active hepatitis B virus (HBV) or hepatitis C virus (HCV), or active cytomegalovirus (CMV) infection (See [Section 3.2](#)).
- Known history of human immunodeficiency virus (HIV) infection
- *Females only:* Pregnant or breastfeeding

Investigational Product Dosage and Administration

The treatment plan is as follows.

Induction phase:

Agent	Dose	Route	Schedule
Ublituximab	900 mg	IV	Cycle 1: Day 1, Day 8, and Day 15 Cycles 2-6: Day 1
Acalabrutinib	100 mg - Twice daily	Orally	Every day of each cycle
Umbralisib	800 mg - Once daily	Orally	Cycle 1: Days 1-14 Cycle 2-6: Days 1-7

Maintenance phase:

Agent	Dose	Route	Schedule
Ublituximab	900 mg	IV	Every 2 cycles (Cycles 8, 10, 12, 14, 16, 18, 20, 22, 24), on Day 1, starting on Day 1 of Cycle 8
Acalabrutinib	100 mg - Twice daily	Orally	Every day of each cycle

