2.3 Overview and Rationale of Study Design

This is a phase 2 study of BTK inhibitor acalabrutinib and PI3K δ umbralisib in combination with ublituximab (AU2) in treatment-naïve MCL patients.

Patients with previously untreated MCL \geq 65 years; or \geq 50 years and deemed ineligible for aggressive induction therapy or autologous stem cell transplant by the investigator, or unwilling to undergo such therapy; or \geq 18 years with documented del(17p), or TP53 mutation, or complex karyotype (CK) will be enrolled.

As noted in the introduction, older patients with MCL do not have curative options, and current standard chemo-immunotherapy regimens (i.e., BR) are associated with a PFS of <4 years and significant toxicities. Furthermore, chemo-immunotherapy regimens are ineffective in patients high-risk MCL (TP53 aberration and/or CK).

Participants will receive 6 cycles of Induction therapy (1 Cycle = 28 days) using the approved standard dose of acalabrutinib (100 mg PO, twice daily), and a previously demonstrated safe dose of umbralisib (800 mg PO, once

daily, see schedule below) and ublituximab (900 mg IV, on Day 1, Day 8 and Day 15 of the first cycle, and Day 1 of each cycle afterward).

Umbralisib will be administered daily on days 1-14 during cycle 1, followed by daily on days 1-7 with subsequent cycles. This intermittent dosing has been successfully employed with other PI3K inhibitors (ME-401; TIDAL study) and was associated with improved toxicity profile without a compromise in efficacy. This approach is particularly attractive in patients with previously untreated MCL who have an intact immune system and thus are at an increased risk of immune-mediated toxicities with PI3K inhibitors.

Maintenance therapy with anti-CD20 targeting antibodies has become standard approach post-induction in MCL, leading to improved OS [49, 50].

Participants with stable disease or better response at the end of Induction therapy will then receive 19 cycles of Maintenance therapy with the 3 agents, during which ublituximab (900 mg IV) will only be administered every 2 cycles.

Participants may continue therapy with acalabrutinib beyond 25 cycles of protocol therapy at the treating physician's discretion.

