5.0 TREATMENT PROGRAM

5.1 Treatment Program Overview

This is a multicenter, open-label, single cohort, phase 2 study of BTK inhibitor acalabrutinib and PI3K δ umbralisib in combination with ublituximab (AU2) for patients with previously untreated mantle cell lymphoma (MCL).

The trial consists of an Induction phase (6 cycles), followed by a Maintenance phase (19 cycles) for a total of 25 cycles of protocol therapy. Participants with stable disease (SD) or better response at the end of Induction will be eligible to proceed to Maintenance. At the end of Maintenance, participants may be allowed to continue therapy with acalabrutinib per treating physician's decision. For both Induction and Maintenance, each cycle will be 28 days.

Please refer to the [Study Schema](#) for additional details.

Participants who end protocol therapy will undergo follow-up ([Section 5.7](#)). Windows for all assessments and treatments are detailed in [Section 10](#).

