5.2 Cycle Definition

In the absence of a delay due to toxicity, each treatment cycle lasts 28 days with a \pm 3 day window during Induction and 28 days with a \pm 7 day window during Maintenance.

During the Induction phase (Cycles 1-6), Day 1 of each cycle is defined as the first day of administration of ublituximab.

During the Maintenance phase (Cycles 7-25), ublituximab is administered every 2 cycles (every 8 weeks) starting on Day 1 of Cycle 8, and each cycle is defined as 28 days.

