5.3 Treatment Plan

The treatment regimen and schedule are as follows:

Induction phase:

Agent	Dose	Route	Schedule
Ublituximab	900 mg	IV	Cycle 1 : Day 1, Day 8, and Day 15 Cycles 2-6 : Day 1
Acalabrutinib	100 mg - Twice daily	Orally	Every day of each cycle
Umbralisib	800 mg - Once daily	Orally	Cycle 1 : Days 1-14 Cycles 2-6 : Days 1-7

Maintenance phase:

Agent	Dose	Route	Schedule
Ublituximab	900 mg	IV	Every 2 cycles (Cycles 8, 10, 12, 14, 16, 18, 20, 22, 24) , on Day 1, starting on Day 1 of Cycle 8
Acalabrutinib	100 mg - Twice daily	Orally	Every day of each cycle
Umbralisib	800 mg - Once daily	Orally	Days 1-7 of each cycle

Treatment will be administered on an *out-patient* basis (in-patient administration is allowed if deemed necessary by the Investigator).

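### Study Calendar footnote r schedules ublituximab at C26, C28 and C30, after the treatment plan's last infusion (C24) and after maintenance ends (C25)

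*Combined protocol and SAP*

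**What the plan says.** The maintenance ublituximab schedule is listed by cycle number in three places.

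- **Study Calendar, Section 10.0, footnote r:** "Ublituximab infusions are on Day 1 of C8, C10, C12, C14, C16, C18, C20, C22, C24, C26, C28, and C30".
- **Section 5.3, Treatment Plan**, introduced by "The treatment regimen and schedule are as follows": "Every 2 cycles (Cycles 8, 10, 12, 14, 16, 18, 20, 22, 24".
- **Protocol Synopsis, maintenance table:** "Every 2 cycles (Cycles 8, 10, 12, 14, 16, 18, 20, 22, 24), on Day 1, starting on Day 1 of Cycle 8".

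The length of the phase is set elsewhere. Section 5.1 describes induction "followed by a Maintenance phase (19 cycles) for a total of 25 cycles of protocol therapy". Section 5.2 says "During the Maintenance phase (Cycles 7-25), ublituximab is administered every 2 cycles (every 8 weeks) starting on Day 1 of Cycle 8". The calendar's maintenance header also spans C7 to C25, and its next column covers optional continuation on acalabrutinib alone.

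For treatment after Cycle 25, Section 2.3 says "Participants may continue therapy with acalabrutinib beyond 25 cycles of protocol therapy" and Section 12.1 says "Participants may continue therapy with acalabrutinib beyond 25 cycles of Induction + Maintenance therapy". When Section 12.1 sets out the later response assessments, it describes patients beyond 25 cycles as being on oral agents only. Ublituximab is intravenous.

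**The concern.** Footnote r conflicts with the treatment plan, with the synopsis and with the header of the table it annotates. Three of its infusions fall in cycles for which the protocol provides no ublituximab.

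The location matters. Sections 5.1 and 5.5 send sites to Section 10 for the timing of treatments and procedures. The ublituximab row in the calendar gives a starting cycle and a frequency but no stopping cycle, so footnote r is the only cycle-by-cycle infusion list there. The protocol does not say which section prevails when two disagree.

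A site dosing from the calendar could give up to three unplanned infusions. Each would bring steroid premedication (Section 5.4.1) and a risk of infusion reaction (Section 5.5.1). Each would also move the date of the last ublituximab dose, from which the contraception period can run (inclusion criterion 17).

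**Working it through.** This is a matter of counting; no statistical formula is involved.

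**Inputs**

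- Maintenance is C7 to C25 (Section 5.2), 19 cycles after 6 of induction (Section 5.1).
- Ublituximab is 900 mg per infusion. Induction has three infusions in Cycle 1 and one in each of Cycles 2 to 6 (Section 5.3).
- Cycles are 28 days (Section 5.2). Nominal days below assume no delays.

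**The plan's own figures reproduce**

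- Maintenance cycles: 25 − 7 + 1 = 19. Total: 6 + 19 = 25.
- Even cycles from C8 within C7–C25: (24 − 8)/2 + 1 = 9, the same nine cycles listed in the synopsis and Section 5.3.

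**Footnote r**

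- Even cycles C8 to C30: (30 − 8)/2 + 1 = 12. The three not found elsewhere are C26, C28 and C30, all later than C25.
- The protocol provides for ublituximab only in induction and maintenance. For C30 to be a valid infusion, maintenance would have to run to at least C30: 30 − 7 + 1 = 24 maintenance cycles and 6 + 24 = 30 in total, against 19 and 25 stated.

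**Exposure if footnote r were followed in full**

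| | Section 5.3 | Footnote r | Difference |
|---|---|---|---|
| Infusions after induction | 9 | 12 | 3 (3/9 = 33%) |
| Dose after induction | 9 × 900 = 8,100 mg | 12 × 900 = 10,800 mg | 2,700 mg |
| Infusions overall (3 + 5 = 8 in induction) | 8 + 9 = 17 | 8 + 12 = 20 | 3 (3/17 = 18%) |
| Dose overall | 17 × 900 = 15,300 mg | 20 × 900 = 18,000 mg | 2,700 mg |

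**Timing**, with Day 1 of cycle n = 28(n − 1) + 1

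- C24: 28 × 23 + 1 = Day 645
- C26: 28 × 25 + 1 = Day 701
- C28: 28 × 27 + 1 = Day 757
- C30: 28 × 29 + 1 = Day 813
- Last dose later by 813 − 645 = 168 days.
- Cycle 25 ends on Day 28 × 25 = 700. The end-of-maintenance visit has a +7-day window, so Days 700 to 707. A C26 dose on Day 701 could fall inside that window, so not all three extra doses necessarily follow the visit.

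**The case against.** The best counter-argument concerns severity, because the discrepancy itself is plain. The intended schedule can be read from several agreeing places. To give a C26 infusion, a site would have to override the synopsis, Sections 5.2 and 5.3, and the heading of the calendar column covering that period. Few patients could be affected: accrual is capped at 27, the trial may stop after nine evaluable patients, and only those who complete 25 cycles and continue would reach C26. The percentages above are therefore upper bounds and not expected effects. All of that stands.

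Three further points deserve an answer.

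- Section 9.2 mentions a C26D1 blood sample for MRD, so C26 does appear elsewhere. It is a sampling label, apparently for the draw that Section 9.1.3 places at end of maintenance, and it authorises no infusion.
- Pre-dose checks offer some protection. Section 5.5 requires safety assessments before a new cycle starts, and Section 8.1.9 requires same-day confirmation before the drug is mixed. Footnote q ties assessments to infusion days, but the extracted table does not show whether that carries past C25. I claim no monitoring gap.
- Correcting protocol text takes more than a memo. Section 16.7 requires approval by both industry partners and submission to the FDA, and Section 17.3 requires IRB approval before changes are implemented. This bears on how the fix is delivered, not on whether it is needed.

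**Conclusion.** The concern holds. Footnote r is current, operative text and its last three entries are wrong; nothing in the protocol provides for ublituximab after Cycle 25. Because the other sections agree on the schedule, this is a wrong dosing list and not an open design question.

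The effect ranges from 0 to 3 extra infusions per patient. The upper bound assumes that the patient completes 25 cycles and stays on therapy, and that the site follows the footnote over Section 5.3. The nominal dates also assume no treatment delays. The primary analysis of CR at the end of induction (Section 11.2), the sample size and the Simon stopping rule are untouched. It should be fixed because it is a dosing instruction for an intravenous antibody in the section sites are told to use.

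**What to change.** Delete C26, C28 and C30 from footnote r so that its list ends at C24, matching the synopsis and Section 5.3. Send sites a clarifying memo now and make the text change in the next amendment, so that the approvals are sought once.

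The cost is three deleted entries and one memo, with no change to sample size, endpoints or analysis.
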